Even when DCIS patients opt to receive a less intensive treatment such as BCS without radiation therapy, they and their providers need to decide whether to undergo sentinel lymph node biopsy (SLNB). The role of SLNB for DCIS management is controversial in general and needs further scrutiny in particular if patients received BCS without radiation therapy. Significant debates continue about whether SLNB should be performed,⁶⁻⁸ with some experts advocating for its use.^{9,10} Proponents of SLNB cite concerns that occult microinvasive disease within the DCIS may not be detected histologically, with an estimated prevalence of 1.4% to 12%.¹¹ However, among DCIS patients who receive radiation therapy the likelihood of local recurrence with axillary involvement is low,¹² and routine SLNB is not recommended.¹³ Of note, radiation therapy has also been shown to control micrometastasis if present.¹⁴ On the other hand, if we plan to empower DCIS patients to choose less intensive management options, such as BCS without radiation therapy, understanding the role of SLNB will be crucial.

A systematic literature review has shown that evidence gaps exist regarding the benefits of SLNB for DCIS.¹⁵ As far as we know, no study has yet examined SLNB among DCIS patients who received BCS. Because of the current call for less intensive treatment, it is imperative to understand the benefits or harms for DCIS patients who received BCS. A large randomized controlled trial would be providing the best evidence to guide treatment recommendations, but the results would not be available for at least 10 years. Our project will use existing data to swiftly provide comprehensive information about comparative effectiveness across the DCIS care continuum in an observational study setting.

Study objectives

Using the Surveillance, Epidemiology, and End Results (SEER)-Medicare linked data, our project's overarching aims are:

Among older women with DCIS who have received BCS as their first surgery, to compare the outcomes of receiving SLNB vs. not receiving SLNB within 6 months of DCIS diagnosis:

Aim 1: We will determine associations between SLNB and acute/subacute side effects, including lymphedema, pain, and limitation of movement of upper extremity from the first BCS to 9 months post-diagnosis.

Aim 2: We will determine associations between SLNB and long-term outcomes, including breast cancer specific mortality, ipsilateral invasive breast cancer diagnosis, subsequent mastectomy as treated recurrence, and lasting side effects, from >9 months post-diagnosis to death or the end of this study period.

Study design

We will conduct a retrospective cohort study. Using the most up-to-date SEER-Medicare database, we will examine the impact of SLNB on clinical outcomes of women with newly diagnosed DCIS among the Medicare population. The nature of SEER-Medicare linking Medicare claims records to tumor registries participating in the NCI's SEER program allows us to select study population based on precise demographic and clinical characteristics of the patients. In our study, the population is DCIS patients older than 67 years (hereafter referred to as older women) who were enrolled in a fee-for-service Medicare program and resided in the SEER areas from 1998 to 2011 (1998-2013 for Aim 2) and who were followed up to 2012 (2015 for Aim 2).

Methodology

Our study population are generated within the SEER-Medicare linked database. To identify patients with DCIS, we will use histology and behavior codes, which are converted from the ICD-O-3 codes that tumor registries are required to report to SEER for all cases.¹⁶ Specifically, we will identify breast “cancer” patients with in situ tumor behavior (behavior code = 2). DCIS patients will be further limited to those with ICD-O-3 codes consistent with epithelial origin. We select age 67 as a cut-off value because we plan to use two years of claims data to identify patient comorbidities and to control for them in our statistical models, and data is first available at age 65.

Our Aim 1 cohort will include DCIS patients who received BCS as their first surgery (i.e. excluding patients who received mastectomy first). We expect that patients who received BCS with SLNB (compared with those who received BCS without SLNB) would be more likely to end up with mastectomy, and thus would be more likely to have side effects. Findings of the associations between SLNB and mastectomy as the final treatment for DCIS would be informative. We intend to include these patients in Aim 1 so that we can provide a comprehensive picture regarding side effects of SLNB in the context of less intensive managements.

Our Aim 2 will examine the long-term outcomes between patients who received BCS without SLNB and patients who received BCS with SLNB. Patients who received BCS in the beginning yet ended up with mastectomy for their primary DCIS will be excluded. For patients who received BCS plus RT, SLNB will not likely provide any benefits since RT is able to control small lesions. However, we plan to determine the effects of SLNB among patients who received BCS without RT, which will have important clinical implications.

The time period for defining the cohort for the Aim 1 will be between January 1998 and December 2011. Using medical claims for this cohort, we will identify any side effects within a

9-month window (from DCIS diagnosis to 9 months post-diagnosis). The time period for defining the cohort for the Aim 2 will be from January 1998 to December 2012, and patients will be followed from 9 months after DCIS diagnosis through the latest date to which data is available in SEER-Medicare. For instance, the next SEER-Medicare linked dataset will have overall mortality through December 2015, breast cancer specific mortality through December 2013, and claims data (to identify treated recurrence) through December 2014.

We identify interventions and comparators in our study using specific international classification of Diseases, Ninth Revision, (ICD-9) codes, CPT codes and HCPCS codes. We will limit our sample to DCIS patients who received BCS as their first surgery; that is, we exclude patients whose first surgery is mastectomy, because we are only interested in patients who receive less intensive treatment and their outcomes. Because SLNB is performed by a surgeon, we identify it within a window consistent with those used in prior literature to identify breast cancer surgery, that is, between the date of the first BCS and 6 months after DCIS diagnosis. We are aware that patients may receive BCS first and mastectomy later for their primary DCIS. Furthermore, we realize that SLNB may affect whether or not patients receive mastectomy.

Based on the input of our patient and professional advisory committee members, we propose the following outcomes of interest in this project. In Aim 1 we focus on acute/sub-acute side effects. Secondary outcomes include treatment received. In Aim 2, our primary outcomes include breast cancer specific mortality, incident ipsilateral invasive breast cancer occurrence (based on ipsilateral invasive breast cancer from SEER) and treated recurrence (based on follow-up mastectomy). Secondary outcomes include overall survival and lasting side effects. Overall survival, expected to be similar, would be used as a benchmark outcome to check performance of our model.

In addition to the key exposures (interventions and comparators) and endpoints (outcomes of interest), we will further select covariates, including patient demographics, comorbidities, tumor characteristics and prior healthcare utilization, based on prior literature and our experience. We plan to include the following covariates to control for confounding. For patient demographics, we will include patient's age, sex, ethnicity, marital status and years of diagnosis. For geographical and social-economical characteristics, we will include income, education and metropolitan residence. For patient's comorbidities, we plan to include Elixhauser comorbidity index, disability index and prior hospitalization. For DCIS characters, we will include grade, size, comedonecrosis and hormone receptor status. For health care system utilization, we will consider prior influenza vaccination, physician visit, MRI use and surgeon's volume. Last, to control for other treatment patients have received, we will adjust for mastectomy and radiation therapy.

Data management and statistical analysis

We plan to create a dataset for this project. Each patient in the SEER-Medicare dataset has a unique patient identification number. Using this information, we will be able to collect patient demographics and DCIS characteristics from the SEER registry as well as claims data from Medicare on what treatment patients have received or what side effects they have experienced. We will manage the dataset in a suitable manner that fully complies with the SEER-Medicare data use rules and confidentiality.

As a secondary data analysis, we will be unable to prevent missing data from the original dataset. We do, however, set a priori exclusion and inclusion criteria for the creation of our cohort. We

will include only DCIS patients who have available claims data (i.e. are enrolled in fee-for-service coverage) during the period between cancer diagnosis and the end of the follow-up (Aim 1: 9 months after DCIS diagnosis; Aim 2: either death or the last date of claims released by SEER-Medicare). Statistically, we plan to create an “unknown” category to capture those patients who had a missing value. Additionally, we will conduct sensitivity analyses regarding whether or not excluding these patients would change our findings.

To compare baseline characteristics between intervention and control groups, we will conduct standard descriptive statistics using χ^2 tests for categorical variables and t-tests for continuous variables. We will tabulate the frequencies of outcomes of interests by the intervention vs. control group. We will use multivariable analyses to test our hypotheses while controlling for unbalanced covariates, as described below.

We plan to control for selection bias using propensity score matching methodology.¹⁷ Specifically, the propensity score matching will be based on the Mahalanobis distance¹⁸ calculated using age, race, residence in a metropolitan county, comorbidity, prior influenza vaccination or prior visit to a primary care physician (both as proxies for access to care), income, preoperative MRI use, and tumor characteristics. Tumor characteristics include size, grade, comedonecrosis, and estrogen receptor status. By incorporating these factors in matching, we expect to substantially decrease bias and balance the risk for outcomes of interest between the SLNB and non-SLNB groups. We will use 2: 1 matching, as prior literature indicated that this approach results in improved precision without a commensurate increase in bias.¹⁹ To ensure robust and comprehensive matching, matches will be assigned by choosing the two best non-SLNB patient matches for each SLNB patient; when two or more SLNB patients match the same control (that is, have Mahalanobis distances minimized by the same control), one will be randomly selected as a match, and this process reiterates until all SLNB patients have two matched controls. We will assess the validity of the matching by comparing risk factors between the SLNB and non-SLNB groups using χ^2 tests. The difference in outcomes between the control and intervention groups will be estimated in a Kaplan-Meier curve. We will estimate the relative risk in the propensity score matched sample using the standard method for matched-pair data.²⁰ We will use the Cox proportional hazards models to investigate the association between various factors (grade, tumor size, and estrogen receptor status) and outcomes.²¹

For multivariable analyses, we will use conditional logistic regression models for acute/subacute side effects (primary outcomes) and treatment received (mastectomy or radiation therapy; secondary outcomes) in Aim 1, with conditioning on the matched variable. For primary outcomes, we will run 2 models, with or without controlling for treatment received. We will report adjusted odds ratios of SLNB on these outcomes. In Aim 2, we will apply time-to-event models to test whether the intervention is associated with better outcomes, including primary and secondary outcomes. We will report adjusted hazard ratios of SLNB on these outcomes. The proportional hazards assumption will be evaluated for each model using a variety of methods (evaluation of Kaplan-Meier and log(-log) survival plots, Schoenfield residuals, and covariate x time interactions). If the proportional hazards assumption is violated, we will instead use parametric survival models, using AIC and BIC to determine the best parameterization (exponential, Weibull, generalized gamma, Gompertz, lognormal, or loglog). All time-to-event models will incorporate a shared frailty term for the matching group, and will include covariates that are not balanced by matching. These models will allow us to test for association between various factors (grade, tumor size, and estrogen receptor status) and outcomes.

In order to identify suitable patient subgroups that may be able to forego SLNB, we plan to explore the following stratification schemes in Aim 2 analysis: 1. Stratify patients by receipt of radiation therapy; 2. Stratify patients by key DCIS characteristics, including grade, comedonecrosis and tumor size; 3. Stratify patients by their predicted life expectancy, given their age, sex and comorbidities.

Expected outcomes of the study

According to our specific aims, we propose different outcomes of interest. For Aim 1, our primary outcome is the side effect occurrence within 9 months post-DCIS-diagnosis. The side effects include lymphedema, pain and limitation of movement of extremities. Our secondary outcome for Aim 1 is treatment received. We will examine the relationship between SLNB and subsequent treatment received, including mastectomy within 6 months after DCIS diagnosis and radiation therapy within 9 months after DCIS diagnosis. For Aim 2, we propose several primary outcomes. We will measure the breast cancer specific survival with the timeframe from 9 months post-diagnosis to death or end of study period. We will also assess the ipsilateral invasive breast cancer occurrence and treated recurrence, including mastectomy, within the same timeframe. For Aim 2, our secondary outcomes include overall survival (a benchmark outcome to check the performance of analytic models) and lasting side effects.

As for detailed outcome measurements, we expect to have these estimates by the end of the project: 1. the difference in baseline characteristics between the intervention and control groups and χ^2 statistics that suggests difference significance; 2. the propensity score matching results, including matched cohort and the standardized difference that indicates the balance of matching; 3. the estimate in the main analysis, for example odds ratio, rate ratio or hazard ratio, that could represent the association of intervention and outcome; 4. the estimate in the stratified analysis that could describe the association of intervention and outcome in each clinical subgroup.

Duration of the project

We are anticipating the project to be completed within 18 months of time.

Ethical concerns

As a result of the nature of our observational design, we do not anticipate any ethical concerns as we are analyzing existing data. We expect this project will be exempt from full review. However, we will make sure that no member in the project would violate the rules and confidentiality required when analyzing SEER-Medicare database.

References

2. American Cancer Society. Cancer Facts & Figure 2013. Atlanta: American Cancer Soc; 2013

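### Exposure closes at month 6 but Aim 2 starts at month 9 and runs for years, and no rule covers a first SLNB after month 6

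*Combined protocol and SAP*

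**What the plan says.** Study objectives states the contrast for both aims: "to compare the outcomes of receiving SLNB vs. not receiving SLNB within 6 months of DCIS diagnosis". Methodology applies it to claims. SLNB is searched for "between the date of the first BCS and 6 months after DCIS diagnosis", and the reason given is that "we identify it within a window consistent with those used in prior literature to identify breast cancer surgery".

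The outcome windows run longer. For Aim 1, Study objectives counts "limitation of movement of upper extremity from the first BCS to 9 months post-diagnosis", Methodology describes a "9-month window (from DCIS diagnosis to 9 months post-diagnosis" span, and Expected outcomes of the study says "our primary outcome is the side effect occurrence within 9 months post-DCIS-diagnosis". For Aim 2, Methodology has women "followed from 9 months after DCIS diagnosis through the latest date to which data is available in SEER-Medicare". Side effects in Aim 2 are not primary: "Secondary outcomes include overall survival and lasting side effects". The Aim 2 primary outcomes are breast cancer mortality, ipsilateral invasive cancer and treated recurrence.

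Methodology removes from Aim 2 women who converted to mastectomy for the primary DCIS. Data management and statistical analysis specifies 2:1 matching, conditional logistic regression for Aim 1 and time-to-event models with a shared frailty term for Aim 2. No section says what happens to a woman whose first SLNB comes after month 6. None states censoring of lasting side effects at later nodal surgery, mastectomy or a second breast cancer.

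**The concern.** There are two separate problems, both mainly in Aim 2.

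The first is misclassification at baseline. Methodology describes Aim 2 as a comparison of BCS with and without SLNB, with follow-up from month 9. A woman with a first SLNB in month 7 has had the procedure by then, yet the 6-month rule puts her among the controls. Her status is known before she contributes any follow-up.

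The second is what lasting side effects measure. Suppose a control recurs in year 3, has her first nodal surgery then and develops lymphedema. On a plain reading she is an event in the no-SLNB group. Arm symptoms after recurrence surgery in an SLNB patient would likewise count with the effects of her initial SLNB. The hazard ratio then blends the initial procedure with downstream care, and the plan does not say which of these it is meant to describe. Elsewhere the plan does recognise that further surgery brings side effects: Methodology expects them after conversion to mastectomy, and the Aim 1 models are run with and without treatment received. Late nodal surgery has no comparable provision.

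At stake is the harm side of the SLNB decision. Late SLNB in controls can pull the estimate toward no effect.

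**Working it through.** The plan gives no sample size, side-effect rate or late-SLNB rate, so there is no figure to reproduce. All rates below are assumptions.

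**1. The windows side by side (months from diagnosis)**

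| Item | Starts | Ends |
|---|---|---|
| SLNB exposure | first BCS | 6 |
| Aim 1 side effects | diagnosis or first BCS | 9 |
| Aim 2 outcomes | 9 | death or end of data |

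The Aim 1 gap is at most 9 − 6 = 3 months. In Aim 2, Methodology gives entry from January 1998 and claims through December 2014. The earliest patients therefore have October 1998 to December 2014, about 16 years, in which later surgery can occur.

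**2. Dilution when only controls are affected**

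Let p0 and p1 be the side-effect risks without and with SLNB, c the share of controls with late SLNB, and f the share of the excess risk that falls inside the outcome window. Late SLNB is assumed to carry the same harm.

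- Control risk = p0 + c·f·(p1 − p0)
- Observed risk difference = true risk difference × (1 − c·f)

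With p0 = 2%, p1 = 6% and f = 1, the true risk ratio is 0.06/0.02 = 3.0:

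- c = 2%: 0.06/0.0208 = 2.88
- c = 5%: 0.06/0.022 = 2.73
- c = 10%: 0.06/0.024 = 2.50

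In Aim 1 a late-SLNB control has at most three months in which to show an effect. Taking f = 1/3 (by analogy with 3 of 9 months), c = 2% gives 0.06/0.02027 = 2.96.

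Aim 1 reports odds ratios. With p0 = 5% and p1 = 10%, the true odds ratio is (0.10/0.90)/(0.05/0.95) = 2.111, and the same formula gives:

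| c | OR, f = 1/3 | OR, f = 1 | Risk difference kept, f = 1/3 | Risk difference kept, f = 1 |
|---|---|---|---|---|
| 1% | 2.104 | 2.089 | 99.7% | 99.0% |
| 5% | 2.075 | 2.005 | 98.3% | 95.0% |
| 10% | 2.039 | 1.909 | 96.7% | 90.0% |
| 20% | 1.972 | 1.741 | 93.3% | 80.0% |

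Halving the risk difference would need c·f = 50%. Since c·f cannot exceed 1, this mechanism cannot reverse the sign.

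**3. Aim 2 hazard ratio, controls only**

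Observed HR ≈ HR/(1 + c·(HR − 1)). This treats late-SLNB controls as exposed from the start, so it overstates the dilution.

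| c | True HR 2.0 | True HR 1.5 |
|---|---|---|
| 1% | 1.98 | 1.49 |
| 5% | 1.90 | 1.46 |
| 10% | 1.82 | 1.43 |
| 20% | 1.67 | 1.36 |

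**4. Aim 2 when later surgery adds events in both groups**

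Let it add a0 to the control risk and a1 to the SLNB risk. The ratio becomes (p1 + a1)/(p0 + a0). It moves toward the null if a1/a0 is below p1/p0 and away from it if above. With the 2% and 6% risks the threshold is 3. The documents give neither a0 nor a1, so the net direction cannot be fixed.

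**The case against.** The strongest defence is that a 6-month exposure window defines a comparison of initial strategies, stated openly and with a reason. Recurrence is itself an Aim 2 outcome, so nodal surgery for a recurrence may be a consequence of the first choice, and its side effects belong to that choice. This stands. It is why the all-follow-up analysis should be kept. It does not cover SLNB in months 6 to 9, which precedes the start of Aim 2 follow-up, and it does not excuse leaving the question unstated.

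A second defence is that removing or censoring women by later events conditions on the future. For Aim 1 this is right: months 6 to 9 lie inside the outcome window, and dropping those controls after matching would break 2:1 sets for little gain. For Aim 2, months 6 to 9 are pre-baseline, so the objection does not apply to the landmark. Censoring after month 9 may be informative, so it can only be a companion analysis.

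Third, the Aim 2 exclusion for conversion to mastectomy may already remove some late nodal surgery, and the plan does not define lasting side effects. Counting new lymphedema after year 3 is therefore a plain reading, not a stated rule. Both points are fair, and both limit the size of the problem.

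A reader might infer that the rule hides SLNB harm in both aims. The documents do not support that. They give no rates, and the assumed ones weaken the estimate without concealing it. In Aim 1 there is also an opposing pull: outcomes count from diagnosis or first BCS while SLNB may come as late as month 6, so side effects before SLNB are credited to the SLNB group.

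**Conclusion.** The point holds as a gap in specification that is cheap to close. Women with a first SLNB in months 6 to 9 are misclassified when Aim 2 begins, and lasting side effects combine the initial SLNB with later surgery in either group.

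Dilution toward the null is possible if late SLNB carries the same harm, but its size is unknown. At an assumed 5% of controls, the risk difference keeps 95.0% of its true value when all the excess is captured, and 98.3% when one third is. The effect is probably small in Aim 1. In Aim 2 the net direction is not established, because recurrence surgery can add events to both groups.

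The side-effect estimates are not shown to be invalid. The absence of censoring at mastectomy or invasive recurrence is no fault for the Aim 2 primary outcomes of treated recurrence and ipsilateral invasive cancer, where those are the events themselves.

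**What to change.** - **Aim 2 exposure:** classify at the month-9 landmark. Exclude women with a first SLNB between months 6 and 9 from the no-SLNB pool before matching, so that matched sets stay intact.
- **Lasting side effects:** keep the all-follow-up analysis. Add a companion analysis that censors at the first nodal surgery, mastectomy or SEER second breast cancer after month 9. State that the first describes the initial strategy with its downstream care and the second the initial SLNB itself.
- **Reporting:** give the number and timing of SLNB after month 6 by group. For Aim 1 this count is enough.

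The cost is modest programming. The plan already requires fee-for-service claims through the end of follow-up, so the records are in hand. The downsides are slightly fewer controls and possibly informative censoring, which is why the censored analysis accompanies the main one and does not replace it.

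### Controls are defined only by the absence of SLNB, so any woman with axillary dissection and no SLNB claim would count as unexposed, and the side-effect comparison could be biased toward no harm

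*Combined protocol and SAP*

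**What the plan says.** The Study objectives compare women by SLNB status alone: "to compare the outcomes of receiving SLNB vs. not receiving SLNB within 6 months of DCIS diagnosis". The Methodology section looks for SLNB "between the date of the first BCS and 6 months after DCIS diagnosis". Under Data management and statistical analysis, each SLNB patient is matched to two non-SLNB patients.

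The Aim 1 primary outcomes are "acute/subacute side effects, including lymphedema, pain, and limitation of movement of upper extremity from the first BCS to 9 months post-diagnosis". In Aim 2, "Secondary outcomes include overall survival and lasting side effects", with the same exposure contrast.

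Two surgical exclusions appear in the Methodology section. For the whole sample, "we exclude patients whose first surgery is mastectomy". For Aim 2, "Patients who received BCS in the beginning yet ended up with mastectomy for their primary DCIS will be excluded". Neither concerns the axilla.

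On coding, the plan says: "We identify interventions and comparators in our study using specific international classification of Diseases, Ninth Revision, (ICD-9) codes, CPT codes and HCPCS codes". No code list is given. On concurrent treatment, the plan says that "to control for other treatment patients have received, we will adjust for mastectomy and radiation therapy". The matching variables cover demographics, comorbidity, access to care, preoperative MRI and tumor characteristics. None of them describes axillary surgery.

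**The concern.** The plan's purpose is to inform women choosing less intensive treatment and to find subgroups who could go without SLNB. For that purpose the useful reference group is women whose axilla was left alone. A control group defined only by the absence of SLNB can also hold women who had a different axillary operation.

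This matters because lymphedema, pain and restricted arm movement are the Aim 1 primary outcomes, and they are harms that axillary surgery can be expected to cause. If dissection carries more of these harms than no axillary surgery, each such control raises the reference risk and SLNB looks safer than it is. The error is in the falsely reassuring direction, on the primary outcome of Aim 1. Nothing later in the plan removes it, because dissection enters neither the matching nor the models.

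**Working it through.** **Is the gap in the text?** Each place where dissection could have been handled was checked:
- Exclusions (Methodology): mastectomy as first surgery and, in Aim 2, later mastectomy for the primary DCIS. Dissection is absent.
- Exposure definition (Study objectives, Methodology): SLNB present or absent in the window. Dissection is absent.
- Matching list (Data management and statistical analysis): no axillary variable.
- Adjustment for other treatment: mastectomy and radiation therapy only.
- Sensitivity analyses: the one described concerns missing values.

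A woman with BCS, dissection and no SLNB claim therefore qualifies as a control under the written rules.

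**How large could the bias be?** The plan gives no sample size, event rate or share of women with dissection, so there is no figure to reproduce. All inputs below are assumptions:
- f = share of matched controls with dissection and no SLNB
- p0 = risk with no axillary surgery
- pS = risk after SLNB
- pA = risk after dissection

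Control risk: pC = (1 − f) × p0 + f × pA.
Odds ratio (the plan's Aim 1 measure): OR = [pS/(1 − pS)] / [pC/(1 − pC)].

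This is a marginal odds ratio. It ignores the conditioning on matched sets.

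Worked case with p0 = 3%, pS = 6%, pA = 15%, f = 5%:
- pC = 0.95 × 0.03 + 0.05 × 0.15 = 0.036
- OR = (0.06/0.94) / (0.036/0.964) = 1.71
- With f = 0, OR = (0.06/0.94) / (0.03/0.97) = 2.06

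| p0, pS, pA | f = 0 | 1% | 2% | 5% | 10% | 15% |
|---|---|---|---|---|---|---|
| 3%, 6%, 15% | 2.06 | 1.98 | 1.91 | 1.71 | 1.46 | 1.27 |
| 3%, 6%, 20% | 2.06 | 1.95 | 1.85 | 1.59 | 1.29 | 1.09 |
| 5%, 7.5%, 15% | 1.54 | 1.51 | 1.48 | 1.39 | 1.27 | 1.17 |
| 10%, 13%, 20% | 1.34 | 1.33 | 1.32 | 1.27 | 1.21 | 1.15 |

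Relative to f = 0, the odds ratio falls by about 1% (1 − 1.33/1.34) to 10% (1 − 1.85/2.06) at a share of 1% to 2%. At 5% it falls by 5% (1 − 1.27/1.34) to 23% (1 − 1.59/2.06).

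The share that would erase the difference is f = (pS − p0)/(pA − p0). In table order this is 0.03/0.12 = 25%, 0.03/0.17 = 18%, 0.025/0.10 = 25% and 0.03/0.10 = 30%.

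**A second set of assumed rates, as risk ratios.** Take p0 = 2% and pS = 5%, so RR = 2.5 with clean controls. For f = 2%, 5% and 10%:
- pA = 15%: pC = 0.0226, 0.0265, 0.033; RR = 2.21, 1.89, 1.52
- pA = 25%: pC = 0.0246, 0.0315, 0.043; RR = 2.03, 1.59, 1.16

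**Does dissection after SLNB cancel the bias?** Those women stay in the SLNB group. In the first scenario, with 5% dissection in that group, its risk is 0.95 × 0.06 + 0.05 × 0.15 = 0.0645. With 5% dissection in both groups the OR is 1.85, against 2.06 with none in either group and 2.23 with dissection in the SLNB group only. The offset is partial.

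**The case against.** Several points on the other side have force.

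- **No count.** A reader might infer that the control group is in fact contaminated, perhaps because diagnoses start in 1998. The documents do not support this. They report no woman with dissection and no SLNB, and say nothing about how dissection was used over the period. This point stands, so the concern is conditional.
- **Unlisted codes.** The plan says that comparators, too, are identified by procedure codes, and the list might screen out dissection. It might, but no text says so, and the written definition does not.
- **Assumed size.** Every rate is assumed, and at a 1% to 2% share the effect is small. This stands. A reader might also infer that the bias could hide or reverse the SLNB effect. In the odds-ratio scenarios, erasing the effect needs a share of 18% to 30%, and the documents give no basis for a share that high.
- **Partial mitigation.** Aim 1 primary models are fitted both with and without adjustment for mastectomy or radiation therapy, which may absorb some dissection done at completion mastectomy. Aim 2 drops women who went on to mastectomy. Dissection with breast conservation remains unaddressed.
- **A deliberate contrast.** SLNB versus no SLNB could be read as a pragmatic choice. That fits poorly with a plan that restricts itself to less intensive treatment and asks who can forgo SLNB.
- **The obvious remedy is biased.** A tempting step is to drop every control with dissection up to 6 months and keep dissection after SLNB in the SLNB group. That conditions on a post-baseline event in one arm only, can overstate SLNB harm, and conflicts with the stated choice to keep in Aim 1 women who end up with mastectomy. This stands and shapes the fix.

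**Conclusion.** The concern holds in conditional form. The written comparator admits women with dissection and no SLNB claim, and no matching or modeling step deals with them. Given that such women exist and that dissection carries more risk of these outcomes than no axillary surgery, the bias in the SLNB estimate from this source is toward no harm. It affects the Aim 1 primary outcomes and the lasting side effects in Aim 2.

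The size cannot be determined from the documents. It is minor if 1% to 2% of controls are affected and material from about 5%. The sponsor can count these women in the claims before any outcome is analyzed. The change should be made, but the documents do not show that the planned result would be wrong.

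**What to change.** 1. List the codes for SLNB and for axillary dissection.
2. Before matching, exclude women whose axillary procedure at the first BCS was a dissection without SLNB, so that the comparator has no axillary surgery at first BCS.
3. Keep women with later dissection, for example at re-operation or completion mastectomy, in their assigned group in both arms, so that no post-baseline exclusion falls on one arm alone.
4. Report the number excluded and the number with dissection in each group.
5. Pre-specify two sensitivity analyses: (a) exclude all dissection without prior SLNB in the window to 6 months; (b) retain all dissection-only women as controls, as the current text would.
6. Apply the same definition to lasting side effects in Aim 2.

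The cost is one more code list applied to claims already held, two extra model runs and the loss of some controls. If the count is near zero, little is lost and the question is closed.
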